Drug-Drug Interactions (DDIs)	
For a complete listing of permitted and prohibited concurrent medications for RPV and RPV LA, refer to Section 6.5.
 
RPV LA should not be co-administered with the following medicinal products, as significant decreases in RPV plasma concentrations may occur (due to CYP3A enzyme induction), which may result in loss of therapeutic effect of RPV LA.
 
 - the anticonvulsants carbamazepine, oxcarbazepine, phenobarbital, phenytoin - the antimycobacterials rifampicin, rifapentine, rifabutin - the glucocorticoid systemic dexamethasone, except as a single dose treatment - St John's wort (Hypericum perforatum). 
Of note, evidence to date indicates that clinically relevant DDIs with RPV LA and other antiretrovirals are unlikely to occur.
 
Oral RPV administration only:
 
 - Antacid products containing divalent cations (e.g., aluminum, calcium, 	
 • All participants will be informed of prohibited medications throughout the study and updates provided as needed via informed consent.

Potential Risk of Clinical Significance	Summary of Data/Rationale for Risk	Mitigation Strategy
	
and magnesium) must be taken at least 2 hours before or at least 4 hours after RPV.
 
 - H2-antagonists must be taken at least 12 hours before or at least 4 hours after taking RPV. - RPV should not be co-administered with proton pump inhibitors, such as esomeprazole, lansoprazole, omeprazole, pantoprazole, rabeprazole; 
Participants discontinuing a LA regimen may be at risk for developing DDIs many weeks after discontinuing injectable therapy.
	

Inadvertent Intravenous Injection (Accidental Maladministration)
	
As with any intramuscular injection, it is possible that RPV LA can be inadvertently administered intravenously instead of intramuscularly possibly resulting in higher than expected concentrations of RPV shortly after injection and lower concentrations thereafter. This could be due to administrator error, improper injection technique and / or improper needle length used based on body type.
 
In addition, HIV-1 viral suppression may not be effective following accidental intravenous maladministration.
	
 • Training will be provided to all sites on proper injection technique. • Should IM maladministration be suspected at any time (e.g., suspected under or overdose or inadvertent intravenous [IV] dosing), post dose ECG monitoring and vital signs or any other supportive testing may be obtained at the discretion of the investigator, and the medical monitor notified. • Laboratory samples for safety parameters and HIV-1 RNA will be closely monitored in all participants. Additionally, 2-hour post dose PK samples will be obtained at a few early timepoints for determination of RPV concentration and possible pharmacokinetic correlation with safety parameters such as ECG changes and virologic response.

Overall Study Related Risks
		

Venipuncture
	
Participants will be required to have blood samples taken. Risk of bruising, and rarely, infection
	
 • Trained personnel will perform venipuncture

Risks of ECG pad removal
	
Some discomfort and rash may occur where the ECG pads are removed.
	
 • ECGs will be conducted by appropriately trained personnel and effort made to minimize contact time for application of

Potential Risk of Clinical Significance	Summary of Data/Rationale for Risk	Mitigation Strategy
		the pads.
Risk of Treatment Failure	
This study employs a novel 2 drug LA ART maintenance regimen for the treatment of HIV-1 infection that remains experimental. Both IM CAB and RPV have demonstrated antiviral activity in large clinical studies and the two-drug combination has demonstrated sustained antiviral activity in studies, LAI116482 and 200056.
 
Doses of the CAB LA and RPV LA have been selected to achieve exposures that are expected to maintain virologic efficacy on the basis of available data with the oral and LA formulations.
 
Due to administration error, it is possible that a participant could receive an inadequate dose of CAB LA or RPV LA. Sub-therapeutic concentrations of either CAB LA or RPV LA could lead to virologic failure and possibly the development of viral resistance.
	
 • Viral loads and CD4+ cell counts will be closely monitored throughout the study (maintenance and extension phases), allowing for early detection of failing treatment. Where confirmed virological failure occurs, participants would be discontinued from study drugs and transferred to an oral HAART regimen. • Plasma samples will be collected as needed during the injection Phase for determination of CAB and RPV concentration and possible pharmacokinetic correlation with virologic response.

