Hypersensitivity Reactions (HSR)	
Hypersensitivity reactions have been reported as uncommon occurrences with integrase inhibitors (INI), including the closely related compound dolutegravir, and were characterized by rash, constitutional findings, and sometimes, organ dysfunction, including liver injury.
 
While there have been no clinical cases of hypersensitivity to CAB to date, there is a theoretical risk of systemic or severe hypersensitivity reactions with or without hepatic symptoms associated with use of IM CAB. The long exposures anticipated after IM CAB injection may complicate the management of a drug hypersensitivity reaction, were it to occur.
	
 The risk of developing a hypersensitivity reaction post administration of IM CAB will be minimized by the use of a 4-week oral lead-in of oral CAB to determine individual safety and tolerability prior to the introduction of IM CAB. Clinical assessments, laboratory tests (including liver transaminases) and vital signs will be performed throughout this study. Results from these assessments may aid early detection of HSR. Oral CAB will be withdrawn immediately for cases with suspected HSR during the oral CAB lead-in phase and would not proceed to the injection phase. Participants receiving the injection who develop suspected HSR would not receive further injections. During oral (oral bridge) and IM CAB treatment, any HSR reactions that occur would be managed supportively.

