10.6.3. Grade 1 or Grade 2 Toxicity/Adverse Event

Participants who develop a Grade 1 or Grade 2 AE or toxicity may continue IP at the discretion of the Investigator. (NOTE: See Section 10.6 Appendix 6, Specific Toxicities/Adverse Event Management” for exceptions to this guideline). Participants who choose to withdraw from study due to a Grade 1 or 2 AE should have study withdrawal and follow-up evaluations completed.

Participants who develop ALT ≥ 3 times ULN while on study must consult with Medical Monitor prior to initiation or continuation of CAB LA and RPV LA.

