10.6.6.10. Allergic reaction

Participants may continue study drug for Grade 1 or 2 allergic reactions at the discretion of the Investigator. The participant should be advised to contact the Investigator immediately if there is any worsening of symptoms or if further systemic signs or symptoms develop. Antihistamines, topical corticosteroids, or antipruritic agents may be prescribed.

Participants with Grade ≥ 3 allergic reactions that are considered to be possibly or probably related to the study drug should permanently discontinue the CAB LA + RPV LA regimen and the participant should be withdrawn from the study. Participants should be treated as clinically appropriate and followed until resolution of the AE.

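### Suspected hypersensitivity stops study drug at any grade in Section 2.3.1, but Sections 10.6.3 and 10.6.6.10 allow Grade 1–2 reactions to continue and Section 7 does not list it

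*Protocol*

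**What the plan says.** The HSR row of the cabotegravir risk table in Section 2.3.1 describes reactions seen with integrase inhibitors, which "were characterized by rash, constitutional findings, and sometimes, organ dysfunction, including liver injury". For the lead-in it states: "Oral CAB will be withdrawn immediately for cases with suspected HSR during the oral CAB lead-in phase", and such a participant does not go on to injection. For the injection phase: "Participants receiving the injection who develop suspected HSR would not receive further injections". None of this depends on grade. For the oral bridge and injection phases it adds that "any HSR reactions that occur would be managed supportively".

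Appendix 6 works by grade. Section 10.6.3 says: "Participants who develop a Grade 1 or Grade 2 AE or toxicity may continue IP at the discretion of the Investigator", and refers to the specific toxicity entries for exceptions. The nearest entry, 10.6.6.10, says: "Participants may continue study drug for Grade 1 or 2 allergic reactions at the discretion of the Investigator". If matters progress, the participant is told to "contact the Investigator immediately if there is any worsening of symptoms or if further systemic signs or symptoms develop". A mandatory stop begins at Grade 3, where participants with "allergic reactions that are considered to be possibly or probably related to the study drug should permanently discontinue" the regimen.

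The must-discontinue list in Section 7 has entries for rash, liver toxicity and related Grade 4 clinical events. It has none for hypersensitivity.

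**The concern.** The same event can meet a categorical stop in the risk section and a permission to continue in the management section. A clinician handling a reaction is more likely to open Appendix 6 or Section 7 than the risk table. Section 1.3 targets sites that have not delivered this regimen before, so they will depend on the written rules.

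Section 2.3.1 presents the four-week oral lead-in as the way to reduce the risk of hypersensitivity after intramuscular cabotegravir, and warns that long exposure may complicate managing a reaction. Section 8.5.5.3 says both drugs can be detected for up to 12 months or longer after injections stop. A tablet can be stopped; an injection cannot be taken back. The error to prevent is a first or further injection in someone for whom 2.3.1 bars it.

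**Working it through.** The plan gives no figure to reproduce and no arithmetic applies. The check is to set the rules side by side and see which cases no operating rule stops.

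**Step 1. The rules for a suspected HSR graded 1 or 2**

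| Place | Instruction |
|---|---|
| 2.3.1, HSR row | Lead-in: withdraw oral cabotegravir, no progression to injection. Injection phase: no further injections. No grade limit. |
| 10.6.3 | May continue at investigator discretion; exceptions are left to the specific entries. |
| 10.6.6.10 | May continue at investigator discretion; no exception for HSR. Mandatory stop from Grade 3 if possibly or probably related. |
| 7, must-discontinue list | HSR not named. |

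**Step 2. Does 10.6.6.10 cover HSR-type events?** Its text refers to allergic reactions, but it anticipates further systemic signs. Its subsection 10.6.6.10.1 is titled as rash without HSR symptoms and is limited to rash with no systemic or allergic features. A reaction that does have those features therefore falls back on 10.6.6.10. Section 10.6.5 gives HSR guidance only for abacavir in the follow-up phase.

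**Step 3. Remove what other rules already handle.**

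- Rash of Grade 3 or higher, or Grade 2 with systemic involvement, with no compelling alternative cause: mandatory stop (Section 7). In the Section 10.2 grading table a diffuse rash is already Grade 2.
- Rash of Grade 2 or higher with an ALT increase: permanent stop (10.6.6.10.1).
- ALT at or above 3 times ULN: Medical Monitor consultation before starting or continuing injections (2.3.1 and 10.6.3). Suspected drug-induced liver injury with no compelling alternative cause: cabotegravir withdrawn (2.3.1).
- Generalized urticaria, angioedema needing intervention, or mild bronchospasm: Grade 3 in Section 10.2, so stopped under 10.6.6.10 if related.

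Further provisions rest on judgement: progression only if evaluations support it (1.3), stopping if drug is not tolerated (7.1), adverse event as an optional reason to discontinue (7), and assessment of every rash for systemic symptoms (2.3.1, rilpivirine rash row). That last row also lets Grade 1–2 rash continue or be rechallenged on clinical judgement.

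**Step 4. Two cases that remain.**

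- A localized rash (Grade 1) with fever of 38.6 to below 39.3 °C (Grade 2), ALT normal. The combination fits the HSR description in 2.3.1. The rash is below Grade 2, so neither rash rule applies, and the liver rules are not met.
- Mild angioedema with no intervention indicated (Grade 2 acute allergic reaction in 10.2), which the investigator suspects is HSR. There is no rash or liver criterion to meet.

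In both, 2.3.1 stops drug, 10.6.3 and 10.6.6.10 permit it to continue, and Section 7 lists nothing that applies.

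**Step 5. Compare neighbouring risks.** In 2.3.1 the liver injury row points to 10.6.2, and the rilpivirine rash row points to 10.6.6.10.1. Liver toxicity and rash each have a Section 7 entry. The HSR row has no pointer to the management sections and no Section 7 entry, which looks like an omission rather than a choice.

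**The case against.** The best reply is that a site can obey every section at once. Section 2.3.1 is current protocol text and specific to suspected HSR, while Appendix 6 only permits continuing. An investigator who stops breaks no rule. That is correct, and it rules out two stronger readings that a reader might draw: that the protocol has no stop rule for HSR, and that Appendix 6 requires drug to continue. But an investigator who continues can cite Appendix 6, and nothing there points back to 2.3.1.

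A second reply is that allergic reaction and HSR are different terms, and that low-grade allergic reactions in the grading table are mostly localized. This narrows the overlap without removing it, as Step 2 and the two cases show.

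A third is that existing rules already catch most presentations. That also stands. A reader might infer that every Grade 1–2 hypersensitivity reaction goes unmanaged; the rash and liver rules do not support that.

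A reader might also want an expected number of cases. The documents give no rate for suspected Grade 1–2 HSR. A figure built on an assumed rate would also count cases already caught, and would not measure how often drug is then wrongly continued.

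**Conclusion.** The inconsistency is real and narrow. It affects suspected HSR of Grade 1 or 2 that meets none of the rash, ALT or liver injury rules. Such cases should be rare: the HSR row reports no clinical case of hypersensitivity to cabotegravir to date. That statement does not cover reactions that are only suspected or are due to rilpivirine, so it supports rarity but gives no rate. No endpoint, sample size or analysis is affected.

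The conclusion rests on two readings of the text: that the HSR row applies at any grade because it states no limit, and that 10.6.6.10 governs reactions with systemic or allergic features. It merits correction because the wrong action cannot be reversed and the remedy is short.

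**What to change.** Add to 10.6.6.10:

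> The Grade 1 or 2 discretion here and in 10.6.3 does not apply to suspected HSR: withdraw oral study drug during the lead-in and do not proceed to injection, and give no further CAB LA + RPV LA injections (see Section 2.3.1).

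Add to the Section 7 must-discontinue list:

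> Suspected HSR (see Section 2.3.1)

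The entry should not carry the alternative-cause qualifier used for rash and liver toxicity. The HSR row has none, and adding it would leave the protocol with two different rules.

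The HSR row names only cabotegravir in the lead-in. Withdrawing both tablets is consistent with 10.6.1, which requires all antiretrovirals to be held when one is held for an adverse event. That section concerns interruption; the bar on proceeding to injection comes from 2.3.1.

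Suspected HSR during an oral bridge, where 2.3.1 speaks only of supportive management, is for the sponsor to decide and is not part of this change.

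The cost is one sentence, one list entry and an occasional extra discontinuation. A participant already injected would then need HAART and 52 weeks of follow-up (7.1), with the resistance risk of declining drug levels that 2.3.1 describes.

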2.3.1.1. Other Clinically Relevant Information

Additional details concerning safety observations from clinical studies and for which a causal association has not been established or which are of minimal clinical significance may be found in the Investigator's Brochures. Refer to 'Summary of data and guidance for the investigator'.

Seizure

Several cases of seizure have occurred during the cabotegravir program. These cases have had alternative explanations for their occurrence. Overall, there is not convincing evidence that cabotegravir exposure may be causally associated with seizure or with reduction of seizure threshold, due to the low frequency of reports, the confounders present in the cases received to date and lack of any pre-clinical signal or identified plausible mechanism. However, seizure and seizure-like events are considered as AEs of special interest for CAB. Subjects with an unstable or poorly controlled seizure disorder will be excluded from study participation. Report any cases of seizure or seizure like events immediately.

2.3.2. Benefit Assessment

The antiviral activity against HIV-1 of CAB has been well established through in vitro and clinical studies. RPV is an established antiviral agent against HIV-1 in treatment naive participants, with long term durability (>96 weeks in Phase 3 and >240 weeks in Phase IIb).

2.3.3. Overall Benefit: Risk Conclusion

Participants receiving CAB LA + RPV LA are anticipated to benefit from maintenance of virological suppression using LA agents. Participants who receive CAB LA+ RPV LA as monthly dosing will not need to take concomitant daily oral antiretroviral therapy. Adherence in these participants is expected to be improved and will be directly observed during IM injections. Efficacy of this two-drug regimen, as IM agents, has been demonstrated through Week 96 of the ongoing 200056 study ([Margolis, 2018](#)).

Taking into account the measures taken to minimize risk to participants participating in this study, the potential risks identified in association with the CAB LA and RPV LA regimen and the study as a whole are justified by the anticipated benefits that may be afforded to virologically suppressed, treatment-experienced participants with HIV-1 infection.

The questionnaires and interviews to be administered to clinical staff and study participants are not associated with additional risk.

3. OBJECTIVES AND ENDPOINTS

Objective	Endpoint
Primary	

To evaluate acceptability, appropriateness, and feasibility of delivering CAB+RPV LA
	
Acceptability of Intervention Measure (AIM), Intervention Appropriateness Measure (IAM), and Feasibility of Intervention Measure (FIM). Assessed quantitatively by staff study participants at baseline- prior to any Month 1 visits, after at least 4 monthly facilitation calls and upon completion of all Month 12 visits at that site.
 
Acceptability of Intervention Measure (AIM) and Intervention Appropriateness Measure (IAM). Assessed quantitatively by patient study participants at Month 1 prior to first injection, Month 4 and Month 12

Secondary	

To evaluate organizational facilitators and barriers
	
Facilitators/Barriers: Semi-Structured Interview (SSI) conducted with staff study participants at baseline- prior to any Month 1 visits, after at least 4 monthly facilitation calls and upon completion of at least 50% of Month 12 visits at that site.
 
Barriers, facilitators and best practice sharing amongst clinics assessed by short-term facilitation (coaching calls) for at least 6 months. These will be a combination of structured questions and open-ended questions.
 
Use of support materials/toolkit assessed via Survey responses of staff study participants prior to any Month 1 visits, after at least 4 monthly facilitation calls and upon completion of all Month 12 visits at a site.
 
Use of support materials/toolkit assessed via Survey responses of patient study participants via Survey responses at Month 1 and Month 4 and Month 12, as well as SSI responses prior to Month 1 and at Month 12.

Objective	Endpoint
Patient Facilitators and Barriers	Facilitators/Barriers: Semi-Structured Interviews (SSI) conducted with patient study participants prior to Month 1 and at Month 12
Implementation Fidelity	
Injections occurring within target window from the expected injection date
 
Use of support materials/toolkit assessed through SSI of staff study participants at Day 1, after at least 4 monthly facilitation calls and upon completion of at least 50% of Month 12 visits at that site.

Implementation Sustainability	Program Sustainability Assessment Tool (PSAT) assessed by staff study participants at Month 12.
To measure patient satisfaction with process (timeliness of visits, length of visit, patient education)	
Patient Survey responses at Month 1, Month 4 and Month 12.
 
Patient SSI responses prior to Month 1 and at Month 12
 
Length of patient visit from arrival until departure from clinic at Month 1, Month 5 and Month 11

Evaluate safety and efficacy measures of CAB+RPV LA	
Proportion of participants with plasma HIV-1 RNA <50 c/mL over time
 
Proportion of participants with confirmed virologic failure (CVF) over time
 
Incidence of treatment emergent genotypic and phenotypic resistance to CAB and RPV in patients with CVF
 
Incidence and severity of AEs and laboratory abnormalities over time
 
Proportion of participants who discontinue treatment due to AEs over time
 
Reported injection site reactions over time
 
Absolute values and changes in laboratory parameters over time

